1.1. Objectives and Endpoints

1.1.1. Primary Objective(s) and Endpoint(s)

The primary objectives of the study are as follows:

- Assess the clinical remission rates associated with TD-1473 compared to placebo treatment at mWeek 44
- Assess the safety and tolerability of TD-1473 with up to 44 additional weeks of treatment

The primary endpoint is clinical remission by adapted Mayo score components at mWeek 44

1.1.2. Secondary Objective(s) and Endpoint(s)

The key secondary objectives of the Study are to assess the rates of the following associated with TD-1473 compared to placebo treatment:

- Clinical response, endoscopic healing, symptomatic remission, and mucosal healing at mWeek 44
- Corticosteroid-free remission at mWeek 44
- Maintenance of clinical remission at mWeek 44 in those who were in clinical remission at mWeek 0

As the study was terminated early only the following secondary endpoints will be analyzed:

[figure not shown]
- Clinical response by adapted Mayo score at mWeek 44
- Endoscopic healing at mWeek 44
- Symptomatic remission at mWeek 44
-

1.2. Study Design

This single protocol includes three studies: a Phase 2b dose-finding Induction Study, a Phase 3 dose-confirming Induction Study, and a Phase 3 randomized-withdrawal Maintenance Study (Figure 1).

Figure 1: Protocol Schema

* Estimated number of subjects for the re-randomized maintenance population

Each of the three studies will utilize a multi-center, randomized, double-blind, placebo-controlled, parallel-group design to evaluate various doses of TD-1473 compared to placebo in subjects with moderately-to-severely active ulcerative colitis (UC).

The Induction Studies will target subjects with moderately-to-severely active UC who demonstrate an inadequate response or failure to tolerate conventional or biologic therapy.

The Maintenance Study will be a randomized withdrawal study targeting subjects with moderately-to severely-active UC who demonstrate a clinical response to induction treatment with TD-1473.

Maintenance Study

In summary, subjects who demonstrate clinical response to a total of 8 weeks of TD-1473 induction therapy, either at Week 8 or Week 16, will be re-randomized. Those who demonstrate response to placebo at Week 8 or those who demonstrate response to a total of 16 weeks of TD-1473 treatment at Week 16 will enter the Maintenance Study on the same study drug treatment as during Induction for the purpose of maintaining blinding. The Maintenance Study consists of treatment for 44 weeks. During the Maintenance Study, subjects must taper their corticosteroid dose using the regimen outlined in Section 6.5.3 if they entered the study on corticosteroids.

The randomization will be stratified by clinical remission status at mWeek 0 using adapted Mayo score component definition, and corticosteroid use at enrollment into the Phase 3 Maintenance Study. In addition, randomization will also be stratified by subjects who reach clinical response after receiving 8 weeks of TD-1473 versus subjects who reach clinical response after receiving placebo during the first 8 weeks and then TD-1473 80 mg during extended induction.

1.3. Treatment Assignment and Blinding

Randomization of the Maintenance Study will be stratified by 3 stratification factors (8 strata): 1) clinical remission status using adapted Mayo score component definition, 2) corticosteroid use at enrollment into the Maintenance Study (4 strata), and 3) subjects who achieved clinical response on TD-1473 during Induction at Week 8 versus subjects who reach clinical response after receiving placebo during the first 8 weeks and then TD-1473 80 mg during extended induction.

1.4. Schedule of Assessments

The schedule of assessments is presented in the protocol.

1.5. Sample Size Determination

Upon completion of the analyses based on the Phase 2b Induction data, the sample size may be refined. Currently, it is estimated that 120 subjects per dose group (360 subjects total) will provide at least 90% disjunctive power to demonstrate at least one of the two TD-1473 doses is effective compared to placebo for the primary endpoint of clinical remission at Maintenance Week 44 under the following assumptions:

- Hochberg step-up procedure adjustment for multiple comparisons
- Family-wise type 1 error rate to be controlled at 5% (2-sided)
- Clinical remission rate of 15% for placebo at Week 44
- Clinical remission rates of 30% and 40% for the two active TD-1473 doses at Maintenance Week 44

A total of 360 subjects total will provide 80% conjunctive power to demonstrate both doses of TD-1473 are effective compared to placebo for clinical remission at Maintenance. In addition, 360 subjects total will also provide adequate power (at least 80%) to demonstrate that at least one of the two TD-1473 doses is effective compared to placebo for the key secondary endpoints of symptomatic remission and endoscopic healing at Maintenance Week 44.

It is estimated that with 880 subjects enrolled in the Induction studies, approximately 400 subjects will be eligible for re-randomization into the Maintenance study. However, about 30 of these 400 subjects will be assigned to the dose that is de-selected based on the analyses of the Phase 2b Induction Study data and therefore not included in the primary efficacy analysis population of the Phase 3 Maintenance Study. In addition, approximately 170 subjects will also enter Maintenance and continue to receive the same treatment as assigned in the Induction study in order to maintain blind. These subjects will also not be included in the primary efficacy analysis population of the Phase 3 Maintenance Study.

2. ANALYSIS SETS

Table 3: Analysis Sets

Analysis Set	Definition	Treatment Assignment
Safety	
The Safety analysis set will include all subjects who received at least one dose of study drug (TD-1473 or placebo) in the Maintenance study.
 
The Safety analysis set is the primary analysis set for safety analyses.
	Actual Treatment received
ITT	
The ITT set comprises all randomized into the Phase 3 Maintenance study.
 
Note: Subjects who demonstrate clinical response to a total of 8 weeks of TD-1473 induction therapy, either at Week 8 or Week 16 are eligible to be re-randomized into the maintenance study.
	Randomized treatment
mITT	
The mITT set comprises all randomized into the Phase 3 Maintenance study who were also treated.
 
Note: Subjects who demonstrate clinical response to a total of 8 weeks of TD-1473 induction therapy, either at Week 8 or Week 16 are eligible to be re-randomized into the maintenance study.
	Randomized treatment

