3. STATISTICAL ANALYSES

3.1. General Considerations

All data from scheduled and unscheduled visits will be presented in the subject listings.

However, unless noted otherwise, only data from scheduled visits will be included in the summaries, statistical analysis, and calculation of derived parameters. All assessments will be summarized using CRF visits.

Summary tables and listings (e.g., post text tables and individual subject data listings are prepared according to ICH Guideline E3) include a “footer” providing explanatory notes.

Continuous variables will be summarized using an 8-point descriptive summary (number of subjects [n], mean, standard deviation [SD], median [Q2], interquartile range [25th percentile Q1, 75th percentile Q3], minimum, and maximum) unless otherwise indicated. Categorical variables will be summarized by frequency and percentage of subjects in each category. For safety assessments, summary statistics will be reported by treatment.

Analyses and tabulations will generally be prepared using SAS®, version 9.4 or later.

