3.7. Safety Analyses

The analysis of safety and tolerability data includes an overall summary of tolerability, adverse event preferred terms by body/organ system, drug exposure (duration of treatment), dosing information/compliance, clinical laboratory results, vital signs and ECGs.

For all safety analyses, the safety analysis population will be used.

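### Maintenance safety tables pool re-randomised subjects with subjects who continued their Induction drug, and no safety table shows the randomised arms

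*SAP*

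**What the plan says.** Maintenance SAP section 2 (Table 3) defines the safety population: "The Safety analysis set will include all subjects who received at least one dose of study drug (TD-1473 or placebo) in the Maintenance study". The treatment assignment given for that set is "Actual Treatment received". Section 3.1 adds: "For safety assessments, summary statistics will be reported by treatment". Section 3.7 adds: "For all safety analyses, the safety analysis population will be used".

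Section 1.2 of the same SAP and protocol section 3.1 describe three routes into Maintenance:

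- Responders to a total of 8 weeks of TD-1473 are re-randomised to placebo or TD-1473. They include subjects who took placebo for 8 weeks and then TD-1473 80 mg for 8 weeks.
- Week 8 placebo responders stay on placebo.
- Responders after 16 weeks of TD-1473 stay on their dose.

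The last two groups are not re-randomised. The protocol keeps them out of the primary efficacy population, and the Maintenance SAP's ITT and mITT sets contain only randomised subjects.

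On planned numbers, section 1.5 says that "approximately 400 subjects will be eligible for re-randomization into the Maintenance study", that "about 30 of these 400 subjects will be assigned to the dose that is de-selected", and that "approximately 170 subjects will also enter Maintenance and continue to receive the same treatment as assigned in the Induction study". Safety is one of the two primary objectives: "Assess the safety and tolerability of TD-1473 with up to 44 additional weeks of treatment".

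**The concern.** For continuers, treatment follows from the route of entry. Every Week 8 placebo responder lands in the placebo column, and every 16-week TD-1473 responder lands in a TD-1473 column. Prior exposure to TD-1473 is an exclusion (protocol section 4.2, criterion 7k), so continuing placebo responders have never taken the drug. Every re-randomised placebo subject has just come off 8 weeks of it. Each TD-1473 column mixes responders to 8 weeks of drug with slower responders who already have 16 weeks of exposure.

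A reader comparing adverse event or laboratory rates across these columns would be comparing groups that differ in earlier exposure and type of response as well as in current drug. Randomisation protects the comparison only among re-randomised subjects, and no safety table is planned for them alone. Section 3.2 repeats only disposition and demographics on ITT, and section 3.8.1 drops subgroup analyses.

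**Working it through.** **Inputs from the documents**

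- 240 Phase 2b subjects randomised 1:1:1:1, so 180 active and 60 placebo. Phase 3 Induction is planned as 320 active and 320 placebo. Totals: 500 active, 380 placebo.
- Active response 60% (protocol section 8.2, item 3).
- 10% of subjects eligible for re-randomisation decline (item 4).
- Re-randomisation 1:1:1:1 before dose selection (protocol section 3.1).
- Planned flow in Maintenance SAP 1.5: about 400 re-randomised, about 30 of them to the de-selected dose, and about 170 continuing.

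**Assumptions, not in the documents**

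- Placebo response at Week 8, written r.
- Response at Week 16 among active Week 8 non-responders, written q.
- The 10% opt-out also applies to continuers. The protocol states it only for those eligible for re-randomisation.
- Only Phase 2b subjects feed Maintenance. This is inferred from Maintenance SAP section 1: the study stopped for lack of efficacy in Phase 2b, and the abbreviated report covers only Phase 2b Induction and Maintenance.

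**Step 1: reproduce the planned flow**

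Re-randomised = [500 × 0.6 + 380 × (1 − r) × 0.6] × 0.9.

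- r = 0.30: 459.6 × 0.9 = 414.
- r = 0.40: 436.8 × 0.9 = 393.
- Setting the result to 400: 270 + 205.2 × (1 − r) = 400, so r = 36.6%.

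Continuing placebo responders are then 380 × 0.366 × 0.9 ≈ 125. The other 170 − 125 = 45 are 16-week TD-1473 responders. As 500 × 0.4 × 0.9 × q = 180q, q is about 25%.

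Check against a figure not used in the solving: Phase 2b re-randomised per arm = [108 + 36 × (1 − 0.366)] × 0.9 / 4 = 29.4. The plan says about 30, so the flow model fits.

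**Step 2: share of the whole planned Safety set**

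170 / (400 + 170) = 30%. This describes the full 880-subject programme.

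**Step 3: shares with Phase 2b feeders only**

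Placebo column: continuers = 60 × r × 0.9; re-randomised = [108 + 36 × (1 − r)] × 0.9 / 4.

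| r | Continuing | Re-randomised | Non-randomised share |
|---|---|---|---|
| 0.30 | 16.2 | 30.0 | 35% |
| 0.366 | 19.8 | 29.4 | 40% |
| 0.40 | 21.6 | 29.2 | 43% |

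Without the opt-out for continuers, the first and last rows become 18 / (18 + 30.0) = 38% and 24 / (24 + 29.2) = 45%.

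Each TD-1473 column with q = 25%: continuers = 60 × 0.4 × 0.25 × 0.9 = 5.4; share = 5.4 / (5.4 + 29.4) = 15.5%, or about 16%.

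Over r = 25-45% and q = 15-40%, the shares are 31-46% for placebo and 10-23% for each dose.

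**Step 4: what the imbalance can do**

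Suppose continuers and re-randomised subjects differ by 10 percentage points in some event rate (an assumed figure) and the drug has no effect. The pooled columns then differ by 10 × (0.402 − 0.155) ≈ 2.5 points. Over the ranges in step 3 this is 0.9 to 3.6 points. The sign depends on which group has the higher rate.

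**The case against.** The case on the other side is substantial.

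- An all-treated safety set by actual treatment is conventional and matches protocol sections 8.3.1 and 8.8. This stands: the set itself is not a defect. But section 8.8 says who is included. It does not confine the tables to one pooled column per treatment.
- The safety objective names no placebo comparator, section 3.7 specifies no safety test, and even the efficacy p-values are to be read descriptively. This stands and limits the weight of the point. Descriptive tables are nevertheless read across columns.
- The randomised arms are partly visible elsewhere. Disposition on ITT includes reasons for stopping treatment, and the efficacy endpoints are assessed in mITT. This stands, but it does not cover adverse events, AESIs or laboratory results.
- The Phase 2b SAP (section 3.7) lists placebo-to-80 mg subjects separately. That is only a loose precedent: those subjects changed drug within the study, and the listing applies to exposure, compliance and adverse events.

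A reader might infer that the pooling makes TD-1473 look worse, because never-exposed placebo responders dilute withdrawal-related worsening in the placebo column. The documents give no event rates to support this. Early termination for lack of efficacy makes a large withdrawal effect less plausible, and the 16-week responders in the TD-1473 columns are themselves a selected group who might have lower rates.

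**Conclusion.** The point holds as a gap in presentation. The pooled safety columns mix randomised and non-randomised subjects in different proportions by arm, and no safety table shows the randomised arms. Under the stated assumptions, with Phase 2b feeders only, about 35-43% of the placebo column and about 16% of each TD-1473 column would be non-randomised.

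The documents do not support three stronger readings:

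- That a planned randomised 44-week safety comparison has been spoiled. No formal safety comparison is specified, the study stopped early, and 44 weeks is the planned duration rather than necessarily the exposure reached.
- That bias runs in a known direction.
- That about half of the reported placebo column is non-randomised. Full-programme figures would give about 125 continuers against about 123 re-randomised (29.4 + (400 − 117.7) / 3 = 123.5), but that programme is not what the abbreviated report covers.

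Actual Maintenance numbers are not in the documents, so every arm-level share is conditional on the assumed or back-solved response rates.

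**What to change.** Keep the all-treated Safety set, as protocol section 8.8 requires, with its pooled per-treatment columns. In Maintenance SAP section 3.7, add the main safety summaries, at least adverse events, AESIs and laboratory results, for re-randomised treated subjects by arm. The existing mITT set identifies them. Show continued-placebo and continued-TD-1473 subjects (by dose) separately, labelled as not re-randomised.

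The cost is SAP wording and a few more table columns. The downside is small numbers: about 29 per re-randomised arm and about 5 per continued dose under the assumptions above. Percentages in the continued-dose groups would therefore mean little, and counts would be the more useful display there.

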3. STATISTICAL ANALYSES

3.1. General Considerations

All data from scheduled and unscheduled visits will be presented in the subject listings.

However, unless noted otherwise, only data from scheduled visits will be included in the summaries, statistical analysis, and calculation of derived parameters. All assessments will be summarized using CRF visits.

Summary tables and listings (e.g., post text tables and individual subject data listings are prepared according to ICH Guideline E3) include a “footer” providing explanatory notes.

Continuous variables will be summarized using an 8-point descriptive summary (number of subjects [n], mean, standard deviation [SD], median [Q2], interquartile range [25th percentile Q1, 75th percentile Q3], minimum, and maximum) unless otherwise indicated. Categorical variables will be summarized by frequency and percentage of subjects in each category. For safety assessments, summary statistics will be reported by treatment.

Analyses and tabulations will generally be prepared using SAS®, version 9.4 or later.

3.2. Study Subjects

Unless otherwise noted, the safety analysis set is the main analysis set used in the summarization of general (Study Population) analyses. Disposition and Demographics tables will be presented also on the ITT population.

3.2.1. Subject Disposition and Completion Status

A summary of study disposition will be provided by study treatment showing the following:

- Number of subjects randomized
- Number of subjects treated
 - Number of treated subjects who completed the study
 - Number of treated subjects who discontinued early from the study
 - Primary reasons for early study discontinuation, with frequencies
 - Number of subjects who completed treatment
 - Number of subjects who discontinued treatment early
 - Primary reasons for early treatment discontinuation, with frequencies

3.2.2. Demographic and Baseline Characteristics

Demographic data including age, sex, race, ethnicity, weight, height, and body mass index (BMI) will be summarized overall and by treatment group. Sex, race, and ethnicity frequency distributions will be provided.

3.2.3. Protocol Deviations

A listing of important protocol deviations will be presented.

3.2.4. Medical History

A listing of subjects medical history will be provided.

3.2.5. Prior/Concomitant Medications

A listing of all concomitant medications will be presented.

3.3. Primary Endpoint(s) Analysis

3.3.1. Definition of Primary Endpoint

The primary endpoint is:

- Clinical remission by adapted Mayo score components at mWeek 44

The adapted Mayo score (0-9 points) is the sum of three components: stool frequency (0-3 pts), rectal bleeding (0-3 pts), and Mayo endoscopic (0-3 pts) subscores.

Clinical remission by adapted Mayo score requires each of the subscores to meet the criteria defined in [Table 4](#). There will be no imputation of missing components, if a component is missing then the endpoint is missing.

Table 4: Clinical Remission by aMS Definition

Mayo Definition	Stool Frequency	Rectal Bleeding	Endoscopic Findings
Adapted Mayo Score (aMS)	0 or 1	0	0 or 1

3.3.2. Statistical Hypotheses

The primary estimate of interest, clinical remission by adapted Mayo score components at mWeek 44, is used to evaluate the effectiveness of therapy relative to the placebo comparator in the mITT population.

As the 0157 maintenance study was terminated early the study is not powered to detect a difference between the active groups and placebo, all analysis and p-values will be interpreted in a purely descriptive manner.

3.3.3. Main Analysis Methods

The proportions of subjects with clinical remission by aMS definitions will be compared between each TD-1473 treatment group and the placebo group using a fishers exact test.

Summaries of the proportion of subjects in remission will be presented by treatment group and p-values from the fishers exact test for the comparison of each dose of TD-1473 versus placebo.

3.3.3.1. Missing Data Handling

There will be no imputation of missing data.

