3.3.4. Sensitivity Analyses

There will be no sensitivity analyses performed.

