3.7.3.3. Electrocardiogram

Descriptive statistics for ECG parameters (heart rate, RR interval, PR interval, QRS interval, QT interval, and QTcF) and changes from baseline values at each assessment time point to the end of study will be presented by treatment group. The QTcF will be calculated using the Fridericia correction.

Subjects without a postbaseline measurement for a given treatment period will be excluded from the summary statistics (e.g., denominator of the summary statistic) for that time point.

All recorded values for the standard 12-lead electrocardiogram parameters will be presented in a by-subject listing.

Categorical Analyses

The number (percentage) of subjects with absolute ECG values and change from baseline in the ranges shown in Table below will be presented in Electrocardiogram Categorical Summary by Visit and Time Point.

In addition, in the same summary, QTcF will also be summarized by the following categories, Normal (males < 430, females ≤ 450), Borderline (males (> 430, ≤ 450); females (> 450, ≤ 470)) and Prolonged (males > 450, females > 470).

Individual ECG data collected during the study will be presented in a listing. A separate listing of subjects with values of QTcF > 500 msec or an increase > 60 msec will be provided, as necessary.

Investigator Assessment of ECG Readings

The investigators’ assessment of ECGs as normal, abnormal and clinically significant, or abnormal but not clinically significant will be summarized for baseline and for each visit.

Table 6: ECG Interval Categories

Heart Rate (bpm)	Heart Rate Change from Baseline (bpm)	PR Interval (msec)	PR Percentage Change From Baseline (%)	QRS Interval (msec)	QT _c F (msec)	QT _c F change from Baseline (msec)
> 120	≥ 20	≥ 200	≥ 15	≥ 120	Males:	≤ 30
> 130	≥ 30	≥ 220	≥ 25		< 430	>30, ≤ 60
					≥ 430	> 60
					≥ 450	
					≥ 470	
					≥ 480	
					≥ 500	
					Females:	
					< 450	
					≥ 450	
					≥ 470	
					≥ 480	
					≥ 500	

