5. SUPPORTING DOCUMENTATION

5.1. Appendix 1: Changes to Protocol-Planned Analyses

The major changes to the analyses specified in the protocol, dated 14 May 2020, are as follows due to early termination of the study:

- deletion of secondary efficacy parameters corticosteroid free remission, maintenance of clinical remission and mucosal healing. The only exploratory efficacy parameter to be displayed is endoscopic remission.
- Changes in the statistical methodology for the primary, secondary efficacy and exploratory parameters from CMH to fishers exact test due to small sample size

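### The Maintenance SAP drops the protocol rule that missing data and treatment failure count as endpoint not met, defines no treatment failure, and lists neither change in Appendix 5.1

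*SAP*

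**What the plan says.** **Protocol.** Section 8.5.4 (Phase 3 Maintenance) counts a subject with missing data, or who meets a treatment-failure criterion, as not in remission. Section 8.9 applies the same two rules to binary endpoints generally: missing means not met, and an observed success is overridden if treatment failure came first. Sections 6.5.4, 8.5.5 and 8.9 leave the definition of treatment failure to the SAP. Section 8.1 requires changes to the planned analyses to be described in the applicable SAP.

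**Maintenance SAP.** Section 3.3.1 says: "There will be no imputation of missing components, if a component is missing then the endpoint is missing". Section 3.3.3.1 says: "There will be no imputation of missing data". Section 3.4.3.1 carries this over to endoscopic healing, clinical response and symptomatic remission. Section 3.3.2 names the mITT population, and section 2 says "The mITT set comprises all randomized into the Phase 3 Maintenance study who were also treated". Section 3.3.3 compares proportions by Fisher's exact test. Section 3.3.4 adds "There will be no sensitivity analyses performed". No section of this SAP mentions treatment failure or intercurrent events.

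Appendix 5.1 opens with "The major changes to the analyses specified in the protocol, dated 14 May 2020, are as follows due to early termination" and gives two items. One is "deletion of secondary efficacy parameters corticosteroid free remission, maintenance of clinical remission and mucosal healing", with endoscopic remission kept as the only exploratory endpoint. The other is the move from CMH to Fisher's exact test.

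On status, 3.3.2 says "all analysis and p-values will be interpreted in a purely descriptive manner".

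**The concern.** This is a randomized-withdrawal study, so relapse is the outcome of interest. Protocol 6.3.12 takes subjects off study drug when they relapse persistently or repeatedly, so a missing mWeek 44 score can itself be the bad outcome. An analysis of observed cases leaves those subjects out of the rate.

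The second gap is separate. The protocol lets rescued subjects stay on study drug and relies on the SAP to say which rescue use is treatment failure. The Maintenance SAP does not say, so a subject who would have been scored as not met can appear as a remitter. Corticosteroid-free remission, the endpoint that would have shown steroid use among remitters, has been deleted. No sensitivity or supplementary analysis would reveal either effect.

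**Working it through.** **1. The rules side by side**

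| | Protocol 8.5.4, 8.9 | Maintenance SAP | In Appendix 5.1? |
|---|---|---|---|
| Missing at mWeek 44 | Not met | Endpoint missing, nothing imputed | No |
| Success after treatment failure | Not met | No rule, so success | No |
| Definition of treatment failure | Left to the SAP | None | No |

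The Phase 2b SAP, for the same remission definition, carries forward missing components (3.4.3) and leaves COVID-19 discontinuations missing. It sets the other intercurrent events and all remaining missing data to not in remission (3.4.4.2, 3.4.4.3). Its Appendix 5.1 names its own departure from Protocol 8.9.

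**2. Who can go missing.** Under Protocol 6.3.12, a subject without improvement at CFA Visit 3, or with a second flare after loss of response, is taken off study drug. Table 2 schedules endoscopy only at mWeek 44 and not at early discontinuation; the only other Maintenance endoscopy is at a flare visit (Table 3). Maintenance SAP 3.1 summarizes by scheduled CRF visit, so earlier scores do not fill mWeek 44.

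**3. Who can be a remitter after treatment failure.** Subjects given permitted rescue keep attending scheduled visits (6.3.12) and stay on study drug (6.5.4). Those with symptoms after mWeek 36 may be given rescue and still complete (6.3.12). Section 6.5.4 says certain rescue use may be treatment failure, not that all of it is.

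**4. The plan's own figure.** SAP 1.5 claims at least 90% disjunctive and 80% conjunctive power with 120 per group at 15%, 30% and 40%. Simulation with Hochberg and a pooled z-test gives 99.1% and 80.4%, so both claims reproduce. This is context only; those planning rates are reused below because the documents give no others.

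**5. Illustration of dropped subjects (all shares assumed).** Let r be the protocol-rule rate among subjects not cut off by the sponsor, f the share of them lost as failures, and a the share of all subjects cut off by the sponsor, unrelated to outcome.

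- Observed-case rate = r/(1 − f). For r = 15%: f = 20% gives 15/0.8 = 18.8%; 40% gives 15/0.6 = 25.0%; 60% gives 15/0.4 = 37.5%.
- Literal protocol rule over all mITT = r(1 − a). For r = 15%: a = 10% gives 13.5%; 30% gives 10.5%; 50% gives 7.5%.

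Observed-case contrasts, active minus placebo:

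| r, placebo vs active | Protocol rule, no cut-off | f 40% / 40% | f 60% placebo / 30% active |
|---|---|---|---|
| 15% vs 40% | 25 points | 66.7 − 25.0 = 41.7 | 57.1 − 37.5 = 19.6 |
| 15% vs 30% | 15 points | 50.0 − 25.0 = 25.0 | 42.9 − 37.5 = 5.4 |
| 15% vs 15% | 0 points | 0 | 21.4 − 37.5 = −16.1 |

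With 30% lost on active, the contrast is overstated while placebo loss is below 53% (40% dose) or 46% (30% dose), and understated above that.

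**6. Illustration of treatment failures counted as remitters.** SAP 1.5 expects about 30 subjects on the de-selected dose; take 30 per arm, all observed. Each such subject adds 1/30 = 3.3 points. Three on placebo move 5/30 (16.7%) to 8/30 (26.7%), and the contrast with 12/30 (40.0%) falls from 23.3 to 13.3 points. If a = 30% and f = 40%, only 30 × 0.7 × 0.6 ≈ 13 are observed, and each adds 1/13 = 7.7 points.

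**The case against.** Several points on the other side stand.

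- **The denominator.** A reader might infer that it is undefined, since 3.3.2 names mITT while the ECG section (3.7.3.3) states that subjects without data "will be excluded from the summary statistics (e.g., denominator of the summary statistic) for that time point" and the remission section has no such sentence. The documents do not support that inference. An endpoint that is missing and not imputed has no cell in a two-by-two table, so observed cases is the natural reading. An explicit n/N would be a clarification.
- **Disclosure.** Protocol 8.1 asks for changes to be described in the SAP, not in a particular appendix, and the missing-data rule is visible in the body. The removal of the treatment-failure rule is described nowhere. SAP section 1 warns that not all planned analyses will be done, but that does not announce a new derivation for endpoints that are kept.
- **Rescue.** A reader might infer that every rescued remitter is misclassified. Section 6.5.4 allows increases up to the Induction Day 1 dose without mentioning failure. How many mWeek 44 remitters met a failure definition is unknown and could be zero.
- **The protocol rule itself.** Applied literally, it scores subjects cut off by the sponsor's termination as failures, so some departure is reasonable.
- **Existing outputs.** Discontinuation reasons by arm (3.2.1) and a concomitant-medication listing (3.2.5) are planned, and the deletion of corticosteroid-free remission is stated openly. These help a reader but do not change the rates. The Phase 2b plan is a separate document, so a difference from it is not by itself an error.

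**Conclusion.** The conflict is real. The Maintenance SAP replaces the protocol's missing-data rule with what reads as an observed-case analysis, omits the treatment-failure definition it was meant to supply, and records neither change in Appendix 5.1. Subjects withdrawn for relapse without an mWeek 44 score drop out of the rate, and a subject who met treatment failure can be counted as a remitter.

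Neither size nor direction is known. The figures above rest on assumed loss and rescue shares, on lost subjects being non-remitters, on sponsor cut-off being unrelated to outcome, and on planning rates set before the study stopped for lack of efficacy. A reader might infer that the change favors the drug; the arithmetic shows it can go either way.

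The results are descriptive, with no hypothesis testing, so error control is not at issue. What is affected is the reported rates and contrasts. The change is worth making because it is cheap, but no confirmatory claim depends on it.

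**What to change.** 1. State the treatment-failure definition that the protocol leaves to the SAP, for example by saying whether intercurrent events 1 to 5 of Phase 2b SAP 3.3.4.1 carry over. Set subjects who met it before mWeek 44 to not met for the retained binary endpoints, and show by arm how many outcomes this changes.
2. Keep the observed-case table, with explicit n/N and the number missing by arm and by reason (sponsor termination versus other).
3. Add one table in which missing for any reason other than sponsor termination counts as not met, with sponsor-terminated subjects shown separately by arm. A cohort defined by calendar (mWeek 44 window closed, 44 × 7 + 2 = 310 days after mWeek 0, before termination) is one option. It needs a stated termination date; the SAP gives only dates by which last doses and final visits had occurred.
4. List the change from Protocol 8.5.4 and 8.9 in Appendix 5.1.
5. Keep all results descriptive.

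The cost is SAP wording and a little programming on disposition reasons, flare visits and concomitant medications already collected. No new data are needed.
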